1.0 SCHEMA

Prior to lung resection at three weeks after PTC, the patient will receive a dynamic enhanced (i.e., non-contrast, arterial and delayed phase) computed tomography(CT) of the chest. These preoperative studies will be compared with the histologic results from thoracotomy, obtained at least 2 days after PTC and no more than 2 months after PTC to assure thorough necrosis. Evaluations will include dimensions of the resected pathologic specimen's necrotic center and its peripheral rim, compared to the CT findings of vessel proximity, central cavitation and associated healing rim, noting the enhancement of the rim and overall ablation zone. The resected ablation zone will undergo histologic analyses of the tumor region near vasculature, as well as the anterior, posterior, superior, inferior, medial and lateral margins to determine if cancer is present and note the characteristics of the healing rim (e.g., inflammatory infiltrates). If cancer is present in any area, this will be compared to the similar ablation margin on CT to assess any differences in enhancement or nodularity.

Key Inclusion Criteria

1. The patient will be a candidate for a thoracotomy
2. The patient will have a peripheral lung tumor 3.0 cm or less in diameter
3. If primary lung cancer, non-invasive staging or mediastinoscopy will suggest the patient has Stage I disease. If patient has metastatic disease, the lungs will be the only site of metastases.
4. The patient will have a biopsy proven cancer before PTC and thoracotomy, including either a CT-guided needle biopsy diagnosis, a bronchoscopic or transbronchial biopsy.

Treatment Plan

1. The patient will undergo CT-guided PTC with the intent to eradicate the entire tumor(s).
3. The patient will have CXR at weeks 1 and 2 (± 2 days).
4. Approximately 3 weeks after PTC, (2-53 days) chest CT and pulmonary function tests will be performed within 7 days of planned resection.
5. Approximately 3 weeks after PTC (2-60 days) the patient will undergo a thoracotomy with resection of the treated lung, consisting of lobectomy for primary lung cancer or wedge resection with adequate margin for a metastatic lesion. The mediastinal lymph nodes will undergo dissection.
6. The resected ablation zone(s) will be measured and histologic samples taken from all six margins and resected lymph nodes.
7. The pathology results will be compared with the preoperative, post-cryotherapy CTs.

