2.0 OBJECTIVES

The primary objective of the study is to evaluate the histologic result of treating primary lung cancer or solitary metastatic lung cancer after PTC.

The secondary objective is to provide a qualitative assessment of the histology from the ablation and tumor margins, comparing histologic observations with imaging enhancement patterns by computed tomography (CT) before and after PTC. Post-cryotherapy, pre-surgical CT scan dimensions and characteristics (e.g., central necrosis and healing rim) will be qualitatively compared to similar areas of the surgical specimen. In addition, histology samples from anterior, posterior, superior, inferior, medial and lateral areas of the resected tumor will be compared to enhancement zones of the ablation margin for any residual cancer.

A tertiary objective is long term follow up for clinical outcome and overall survival.

A total of ten evaluable patients qualifying in either Cohort A or Cohort B will be included.

Cohort A. Patients who have been diagnosed with Stage I primary peripheral lung cancer less than 3.0 cm in average diameter without prior radiation or chemotherapy.

Cohort B. Patients with metastatic solitary or multiple (≤ 3) peripheral lung lesions less than 3.0 cm in average diameter which have not been treated with radiation or chemotherapy since the new metastatic lesion appeared.

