There are no studies on the efficacy of percutaneous cryotherapy of lung tumors other than chest CT scan or by utilizing PET scan to demonstrate that no residual tumor is present.³⁷ There is no study that histologically demonstrates that the percutaneous cryoablation technique has been able to kill all viable tumor cells, including the potentially misleading breast cancer data which reports insufficient ablation of tumors >1.5 cm but only used 1 probe in all cases³⁸.

This study would resect the ablated lung tissue after a sufficient period of time to assure thorough necrosis by standard hematoxylin and eosin stains (i.e., >1 day), but not so long after cryotherapy that central necrosis can not be differentiated from healing rim (i.e., <60 days). This allows greater flexibility in the recruitment of patients surrounding their scheduled resection. The resected ablation zone will be measured to compare the average diameter in three dimensions with the CT scan dimensions. The diameter of the necrotic tumor and the ablated zone will be measured and compared with these areas on the CT scan. The ablative zone's regions of enhancement or nodularity (i.e., possible residual cancer) will be compared with regions (anterior, posterior, superior, inferior, medial and lateral) from the pathologic analysis of the tumor, including effects upon any adjacent bronchi and vasculature. We expect that all tumor will be eradicated with cryotherapy, but would define success as more than 75% of analyzed tissue being negative for cancer. Radiofrequency ablation frequently leaves residual tumor and recurrence rates range from 12-58%²²⁻²⁴ depending on tumor size and vessel proximity. Our hope is that the percutaneous cryoablation technique will show more thorough destruction of cancer cells.

The usual clinical scenario is that the patient who is receiving percutaneous cryotherapy does not have an operation or cannot have an operation. This study would give us the unique opportunity to resect the tissue, which has received cryotherapy, and determine whether this is a viable treatment option as a primary treatment modality rather than as a last ditch treatment, or treatment of last resort.

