The patient will then undergo a standard thoracotomy for lobectomy for the primary lung carcinoma or a limited wedge resection for metastatic lung cancer. The resected tissue will be forwarded to pathology for analysis of remaining tumor. The patients will also have mediastinal node dissection at the time of operation, a standard staging procedure. The lymph node stations will also be assessed for residual tumor. Lung parenchyma surrounding the area of cryotherapy will also be assessed for any residual damage from the cryotherapy probes and treatment.

The histological analysis of the lung, tissue will then be compared with the CT scan. If there is any residual tumor, this will be correlated with the CT scan. In addition, the lung which had been resected will be assessed for damage from the cryotherapy technique.

Patients will have standard follow-up studies as per their primary lung oncologist. The patient will be requested to have a follow up CT scan of the chest and PET scan at six months for their long term follow up.

In addition to patients being followed by the treating physician at as needed clinic visits patients will be followed yearly for survival.

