7.0 CORRELATIVE / SPECIAL STUDIES

We propose to correlate the patient's CT scan before the operation with the final pathology result.

Any changes that are noted on the CT scan in relation to the pathologic specimen may have predictive value. Imaging studies such as chest CT scan, or PET scan will be a requirement to ensure that no tumor remains after therapy. Since future patients who are not operative candidates will require imaging studies to determine the presence or absence of tumor following therapy, any prediction value of imaging studies will be very important.

The PET scans will be performed and interpreted by [name] [contact]) of Karmanos Cancer Center/Wayne State University, [name].

FDG(F-fluoro-deoxy-D-glucose)- is a radiolabelled glucose used in PET imaging that is transported into the cells. It is accumulated in neoplastic cells at a more rapid rate than normal tissue. Non-neoplastic disease such as granulomatous and inflammatory processes could also accumulate PDG and give false results, there a histologic analysis of cryotreated tissue (both neoplastic and inflammatory processes) needs to be done to evaluate the cryotherapy effect on the neoplasm.

FDG uptake will be measured as Standard Uptake Value (SUV). Standard Uptake Value is calculated by the following formula: $SUV = \text{radioactivity concentration in ROI (Region of Interest)} (\mu\text{Ci/ml}) \text{ divided by injected dose } (\mu\text{Ci})/\text{body weight (kg)}$. The SUV mean will be measured over the whole Region of Interest (ROI). The SUV max will be measured as the uptake in the hottest pixels in the same ROI.

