7.3 Pathological Response

The tumor will be evaluated by a pathologist, [name] [contact]) in the Harper University Hospital , DMC/Wayne State University Pathology Department. The entire resected specimen and the lymph nodes will be re-evaluated for presence of tumor. In addition, the remainder of the treated lung will be analyzed for response to cryotherapy, including damage to lung parenchyma, connective tissue and blood vessel. Any area of hemorrhage will be noted.

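### No CT call per margin is fixed before pathology and no paired CT-by-histology analysis is planned, so any predictive value of CT is open to review bias

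*Combined protocol and SAP*

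**What the plan says.** The CT-histology comparison is described in several places, not always in the same way.

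- **Started by positive histology.** Section 1.0 (Schema): "If cancer is present in any area, this will be compared to the similar ablation margin on CT", with enhancement and nodularity as the features of interest. Section 5.0 has the same order: "If there is any residual tumor, this will be correlated with the CT scan".
- **Not conditional on a positive result.** Schema, treatment item 7: "The pathology results will be compared with the preoperative, post-cryotherapy CTs". Item 6 has "histologic samples taken from all six margins and resected lymph nodes". Section 2.0 says that samples from the six areas "will be compared to enhancement zones of the ablation margin for any residual cancer".
- **Started from CT.** Section 3.4: "The ablative zone's regions of enhancement or nodularity (i.e., possible residual cancer) will be compared with regions" from the pathologic analysis, again listing all six.

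Section 5.0 places a CT about 3 weeks after cryotherapy and before thoracotomy, to assess tumor dimension and residual change. It names no reader and asks for no result by margin. Section 7.3 says "The tumor will be evaluated by a pathologist" but not whether the CT findings are at hand.

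Section 7.0 proposes to correlate the pre-operative CT with final pathology and says that "any prediction value of imaging studies will be very important". Section 9.3 assigns the Section 7.0 studies to secondary objective 2. It then lists point and interval estimates for PET SUVmean, PET SUVmax, CT response rate and pathologic response rate.

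**The concern.** Section 7.0 looks ahead to patients whose tumor will not be resected, where CT must show whether cancer remains. That question needs two things: a CT judgement made without knowledge of the histology, and a count of all margins, including those clean on both. The plan secures neither.

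If a margin is judged on CT once cancer is known to be there, faint enhancement is more easily called suspicious and apparent sensitivity rises. If attention goes mainly to margins that were positive on one test, specificity and the predictive values lose their denominators. Resection after ablation is a rare chance to check CT against tissue, and Section 9.5 expects 60 months to enroll 10 evaluable patients. A judgement not written down before pathology cannot be obtained later without hindsight.

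**Working it through.** **1. What the text fixes.**

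| Needed for a predictive value | In the plan? |
|---|---|
| CT taken before resection | Yes (Schema, 5.0, Study Calendar) |
| Histology at all six margins | Yes (Schema item 6) |
| Comparison over all six regions | Yes in 2.0, 3.4 and Schema item 7; the Schema and 5.0 also have histology-triggered versions |
| CT call at each margin, with a rule for suspicious | No |
| Call recorded before pathology is known | No |
| Pathologist scoring without the CT call | Not stated |
| Analysis pairing CT with histology | No; 9.3 lists separate summaries |

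The CT response rate in 9.3 does not fill the last row. Section 7.2 defines response by disappearance or shrinkage of the lesion, not by enhancement or nodularity at a margin. Two marginal rates also cannot show whether the same margins were abnormal on both tests.

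**2. The plan's own precision.** Section 9.2 gives Wilson 80% half-widths for n = 10:

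h = z·√[p(1−p)/n + z²/(4n²)] / (1 + z²/n), with z = 1.2816.

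At p = 0.50: 1.2816 × √(0.0250 + 0.0041) / 1.164 = 0.188, as stated. The rest of the table reproduces to within 0.001.

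**3. Number of margins.** At one lesion per patient, 10 × 6 = 60. Cohort B allows up to three lesions, so the ceiling is 10 × 3 × 6 = 180. Section 9.2 expects mostly Cohort A, so 60 is used below.

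**4. Expected positive margins.** The plan gives no rate by margin. Its hypothesis is that all tumor is eradicated, which means 0. For assumed rates, treating margins as independent:

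| Rate | Expected of 60 | P(none positive) = (1 − rate)^60 |
|---|---|---|
| 2% | 1.2 | 0.30 |
| 5% | 3 | 0.05 |
| 10% | 6 | 0.002 |
| 20% | 12 | <0.001 |

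**5. Size of review bias (illustration).** Assume true sensitivity 0.60, specificity 0.85 and 10% positive margins. Suppose a reader who knows the histology upgrades half of the missed positive margins.

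- Sensitivity: 0.60 + 0.5 × 0.40 = 0.80.
- Positive predictive value: 0.060/(0.060 + 0.135) = 0.31 becomes 0.080/(0.080 + 0.135) = 0.37.
- Negative predictive value: 0.765/(0.765 + 0.040) = 0.95 becomes 0.765/(0.765 + 0.020) = 0.975.

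The share of missed margins goes from 40% to 20% with no change in the scan.

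**6. What a full table could deliver.** With 3 positive margins, the Wilson 80% half-width for sensitivity is 0.30 at 0.5 and 0.26 at 0.8: weak. Specificity is better placed. If all 60 margins were clean and CT called 9 suspicious, specificity is 51/60 = 0.85. Its half-width is 1.2816 × √(0.002125 + 0.000114)/1.027 = 0.06 if margins are independent. If margins within a patient agree completely (effective n = 10), it is 1.2816 × √(0.01275 + 0.00411)/1.164 = 0.14. Both are below the 0.188 worst case accepted in 9.2.

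**The case against.** The strongest reply is that this is an exploratory, qualitative comparison in a 10-patient pilot. Section 7.0 says only that CT changes may have predictive value, Section 2.0 calls the comparison qualitative, and Section 9.3 expects the histology objective to need little statistics and plans no sensitivity or predictive value. If all tumor is eradicated, sensitivity is undefined and negative predictive value is trivially 100%. Much of this stands: the gap touches no primary result, and sensitivity will be poorly estimated at best. It does not answer everything, because the Section 7.0 correlation falls under secondary objective 2, which is to be summarized statistically, yet no listed summary pairs the two tests.

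Three stronger readings are tempting, and the documents do not support them.

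- A reader might infer from "If cancer is present in any area, this will be compared to the similar ablation margin on CT" that CT margins are read again once cancer is known. The text does not say when the CT is read or by whom, and 5.0 places a CT assessment before surgery.
- A reader might infer that only cancer-positive margins are compared, so that a handful of margins inform instead of 60. The Schema, 2.0 and 3.4 also describe comparisons over all six regions.
- A reader might conclude that the design cannot yield an unbiased predictive value. A locked reading before pathology is fully compatible with it, and the plan never claims to be unbiased.

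Nor does Section 7.3 show that the pathologist knows the CT result; it is silent.

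**Conclusion.** The point holds as a gap in specification. The plan states an interest in CT's predictive value and collects both halves of the data, but fixes no CT call per margin before pathology and plans no paired analysis. Any resulting claim about CT would be exposed to review bias and selective comparison.

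The size cannot be derived from the documents. The shift in sensitivity from 0.60 to 0.80 rests on assumed accuracy, an assumed 10% of positive margins and an assumed upgrade of half of the misses. The precision figures assume one lesion per patient, with margins either independent or fully clustered. The primary endpoint, sample size and safety monitoring are unaffected. The change is worth making because it is cheap now and cannot be made good afterwards.

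**What to change.** **Section 7.0.** Whoever reads the pre-resection CT records suspicious or not suspicious for each of the six margins of each treated lesion, on a form completed and locked before thoracotomy. The form states the rule for a suspicious call, using the enhancement and nodularity features that the plan already names. The pathologist scores each margin without sight of the form.

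**Section 9.3.** Add an exploratory cross-table of CT call by histology over all margins of all evaluable patients, with patient as the cluster and 80% intervals to match 9.2. Report sensitivity only if some margin holds cancer; the false-positive rate (specificity) remains estimable either way. Keep look-back comparisons of positive areas as descriptive only.

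**Cost.** One short form and a few sentences in each section, with no added scan or procedure. The documents name no CT reader, so that role has to be assigned. The order of readings must be kept, and sensitivity will stay imprecise.

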2.0 OBJECTIVES

The primary objective of the study is to evaluate the histologic result of treating primary lung cancer or solitary metastatic lung cancer after PTC.

The secondary objective is to provide a qualitative assessment of the histology from the ablation and tumor margins, comparing histologic observations with imaging enhancement patterns by computed tomography (CT) before and after PTC. Post-cryotherapy, pre-surgical CT scan dimensions and characteristics (e.g., central necrosis and healing rim) will be qualitatively compared to similar areas of the surgical specimen. In addition, histology samples from anterior, posterior, superior, inferior, medial and lateral areas of the resected tumor will be compared to enhancement zones of the ablation margin for any residual cancer.

A tertiary objective is long term follow up for clinical outcome and overall survival.

A total of ten evaluable patients qualifying in either Cohort A or Cohort B will be included.

Cohort A. Patients who have been diagnosed with Stage I primary peripheral lung cancer less than 3.0 cm in average diameter without prior radiation or chemotherapy.

Cohort B. Patients with metastatic solitary or multiple (≤ 3) peripheral lung lesions less than 3.0 cm in average diameter which have not been treated with radiation or chemotherapy since the new metastatic lesion appeared.

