7.4 Follow-Up

All patients who are registered to the trial will be followed for survival regardless of whether the patient completed protocol treatment.

[figure not shown]
[figure not shown]
All adverse events and serious adverse events that are related to protocol treatment will be followed until resolution.

7.5 Evaluable patients.

To be evaluable for this pilot study, the patient must undergo the planned thoracotomy < 12 weeks from percutaneous cryotherapy, as noted in the Study Calendar. Inevaluable patients will be replaced until the statistically required sample size of 10 evaluable patients (as determined in Section 9.2) has been obtained.

8.0 **Figure 1: The 1-2 rule for cryoprobe placements according to tumor size (black circles)**

Using a single cryoprobe requires precise central placement [22] to cover the tumor with ice (darker gray around each probe), let alone lethal ice (smaller dashed line ~5 mm inside ice). Conversely, when more probes are used, the sum of the individual ice projections (darker gray circles) synergistically expand, extending lethal ice (larger dashed line) ~ 5 mm beyond all tumor margins while visible ice (lighter gray circle) projects ~ 10 mm.

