9.0 Statistical Considerations

9.1 Primary objective.

The primary objective of this pilot study is to evaluate the histologic result of treating primary lung cancer or solitary metastatic lung cancer after PTC. The primary statistical objective is to estimate the PTC success rate (p) as defined in Section 3.4, paragraph 6, i.e., that > 75% of the tissue analyzed histologically 3 weeks post-PTC is negative for cancer. The pilot study hypothesis is that all tumor will be eradicated via PTC.

9.2 Sample size.

The target sample size for this pilot study is 10 evaluable patients (defined in Section 7.5) , from Cohorts A and B combined. The 2 cohorts are defined in Section 2.0, and will not be distinguished in this small pilot study. It is expected that most (if not all) patients who enroll will be in Cohort A. Both point and 80% confidence interval (CI) estimates of p , and of the mean % of tissue which is found negative for cancer (TNC) histologically will be calculated. The precision (i.e, half-width of the CI) attainable in the estimate of (p) with $N=10$ evaluable patients will depend on the point estimate of the sample rate (p), in the following manner:

Rate	0.10	0.20	0.30	0.40	0.50	0.60	0.70	0.80	0.90
Precision	0.126	0.156	0.175	0.185	0.188	0.185	0.175	0.156	0.126

With 10 evaluable patients, (p) could be estimated to a precision of 0.188 or better (i.e., smaller) for most values of (p), with 80% confidence. The table values were computed using Wilson 80% confidence intervals in the PASS 2011 software program "Confidence Intervals for One Proportion – New". With 10 evaluable patients, the mean of a continuous endpoint (e.g., the mean % TNC) could be estimated to within 0.437 standard deviation (SD) units, with 80% confidence. Those are reasonable precision and confidence levels for a small pilot study, and should provide sufficiently precise estimates for use in planning a subsequent investigation.

9.3 Secondary objectives.

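### The primary success rule (more than 75% of analyzed tissue negative) has no stated denominator or unit, and on some of the tissue the protocol describes, a fully viable tumor would score as a success

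*Combined protocol and SAP*

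**What the plan says.** **The rule.** In Section 3.4 the investigators "would define success as more than 75% of analyzed tissue being negative for cancer". Section 9.1 points back to that paragraph and restates the criterion as "> 75% of the tissue analyzed histologically 3 weeks post-PTC is negative for cancer". Section 9.2 adds a second estimate of the same kind, the mean percentage of tissue negative for cancer (% TNC). None of these sections names the tissue that forms the denominator, or says whether the percentage is of samples, area or volume.

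**The histology.** It is described differently in three places:

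- Section 1.0, Treatment Plan item 6: "histologic samples taken from all six margins and resected lymph nodes". The schema narrative again takes the margin in each direction and adds a tumor region close to vessels: "The resected ablation zone will undergo histologic analyses of the tumor region near vasculature, as well as the anterior, posterior, superior, inferior, medial and lateral".
- Section 2.0, within the secondary objective: "histology samples from anterior, posterior, superior, inferior, medial and lateral areas of the resected tumor", to be compared with CT enhancement.
- Section 7.3: "The entire resected specimen and the lymph nodes will be re-evaluated for presence of tumor". The rest of the treated lung is also examined there for the effects of cryotherapy.

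**Sizes.** Section 1.0 limits size: "The patient will have a peripheral lung tumor 3.0 cm or less in diameter". The Figure 1 caption (8.0) describes multiple probes as "extending lethal ice (larger dashed line) ~ 5 mm beyond all tumor margins while visible ice (lighter gray circle) projects ~ 10 mm". Section 1.0 plans lobectomy for primary cancer and wedge resection for metastases, and Section 9.2 expects nearly all patients to be in Cohort A, the primary cancers.

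**The concern.** Everything listed above is tissue examined histologically, so each description is a possible denominator for the rule. The choice matters because the rule asks only whether tissue is negative, not whether it once held tumor. Normal lung, the rim of treated lung outside the tumor and uninvolved nodes are negative whatever cryotherapy did. Two pathologists could therefore score the same specimen in opposite ways, each following the protocol. If non-tumor tissue enters the denominator, p and mean % TNC partly measure how much normal tissue was examined. Section 9.2 intends these estimates for planning a later study, so the ambiguity would be carried into it.

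**Working it through.** **1. The plan's own figures.** For a Wilson two-sided 80% interval with n = 10 and z = 1.2816, the half-width is z·√(p(1−p)/n + z²/4n²) / (1 + z²/n). At p = 0.50 this is 1.2816 × √(0.025 + 0.0041) / 1.164 = 0.188, as stated. The other table entries agree to within 0.001. For a mean, t(0.90, 9 df)/√10 = 1.383/3.162 = 0.437 SD, as stated. Neither calculation uses the denominator of the 75% rule, so neither shows what p measures.

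**2. Test case.** Take a tumor at the size limit, 3.0 cm, assumed spherical, with no cell killed. This is a limiting case and not a forecast. Partial kill can only raise the percentage negative, so wherever the fully viable tumor passes, any smaller residue passes too.

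Tumor volume = (π/6) × 3.0³ = 14.1 mL.

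**3. Counting samples.**

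- Six areas of the tumor (2.0): 0/6 = 0% negative. Failure.
- Six ablation-zone margins (1.0), if they lie 5 to 10 mm outside the tumor as the Figure 1 ice extents suggest: up to 6/6 = 100% negative. Success.
- The same six margins plus one positive vessel-adjacent tumor sample (assuming that region gives one sample): 6/7 = 85.7% negative. Success.
- Six positive tumor samples pooled with negative nodes: 18 nodes give 18/24 = 75.0%, which does not exceed 75%; 19 give 19/25 = 76.0%. Nodes alone change the result only in large numbers.

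**4. Entire specimen by volume (7.3).** Fraction negative = 1 − 14.1/V, which exceeds 0.75 when V > 4 × 14.14 = 56.5 mL. For a 2.0 cm tumor (4.19 mL) the threshold is 16.8 mL. The documents give no specimen volumes, so those below are assumed.

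| Assumed specimen volume (mL) | Negative, viable 3.0 cm tumor | Result |
|---|---|---|
| 50 | 71.7% | Failure |
| 100 | 85.9% | Success |
| 200 | 92.9% | Success |
| 400 | 96.5% | Success |
| 800 | 98.2% | Success |

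**5. Ablation zone by volume.** Fraction negative = 1 − (tumor diameter / zone diameter)³.

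| Tumor | 10 mm rim (visible ice) | 5 mm rim (lethal ice) |
|---|---|---|
| 3.0 cm | 1 − (3/5)³ = 78.4%, success | 1 − (3/4)³ = 57.8%, failure |
| 2.0 cm | 1 − (2/4)³ = 87.5%, success | 1 − (2/3)³ = 70.4%, failure |

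With a 5 mm rim only tumors below about 1.7 cm pass. On this frame the result turns on which of the two extents in the Figure 1 caption is used.

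**The case against.** The strongest reply is that the protocol never applies the 75% rule to margins, nodes or the whole specimen. Each of those descriptions has another purpose. The Section 2.0 wording belongs to a qualitative CT comparison. Section 7.3 is headed as pathological response, and Section 9.3 lists a separate pathologic response rate. Node dissection is described in Section 5.0 as staging. Just before the rule, the same paragraph of Section 3.4 speaks of directional regions from pathologic analysis of the tumor, which is the most natural antecedent; on that reading an untreated tumor scores 0/6 and fails. Section 7.3 reads the specimen to detect tumor and attaches no percentage to it.

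Most of this stands. A reader might infer that the protocol gives contradictory definitions of success. It does not: it gives none, alongside several inconsistent candidates. A reader might also infer that any larger sampling frame passes an untreated tumor. The working does not support that: a whole specimen under 56.5 mL fails, an ablation zone with a 5 mm rim fails for 2.0 and 3.0 cm tumors, and the small margin-only frame can pass.

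The reply does not supply a denominator. The directional wording in Section 3.4 concerns the CT comparison, and the same paragraph also measures the whole ablated zone. Section 9.1 adds nothing beyond the cross-reference, and Section 7.3 gives no numerical definition that would separate pathologic response from p.

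**Conclusion.** The concern holds as an undefined denominator and unit for the primary success rule and for mean % TNC, with inconsistent descriptions of the tissue examined. The same fully viable 3.0 cm tumor is a failure on tumor areas (0/6), can be a success on margins outside the tumor (up to 6/6), and is a success by volume in any whole specimen above 56.5 mL (86% to 98% negative at an assumed 100 to 800 mL). On the ablation zone by volume it falls either side of the cut-off: 78% with a 10 mm rim and 58% with a 5 mm rim. With lobectomy expected for most patients, a specimen above 56.5 mL is plausible, but that is an assumption. The volume figures also assume spherical tumors and zones.

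Two further inferences go too far. First, it does not follow that the pilot cannot show whether cryotherapy kills tumor: residual cancer would be looked for throughout the specimen and compared with CT, so it is the summary percentage that is ambiguous. Second, with six samples the rule passes 5/6 (83%) and fails 4/6 (67%), so one positive sample is tolerated. That is a consequence of the investigators' choice of 75% and is not an error.

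**What to change.** In Section 9.1, state one denominator and one unit: the percentage of the original tumor bed that is negative for viable cancer. Define the bed as its center, the six directional areas of the tumor and the vessel-adjacent region, and say how the regional readings combine into one percentage. The center must be named, because the six directional samples alone do not cover it. Use the same definition for % TNC in Section 9.2. Report the ablation rim, surrounding lung and lymph nodes separately, outside both % TNC and the success rule. Align Sections 1.0, 2.0, 3.4 and 7.3 with this wording before specimens are scored.

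The cost is mainly a wording amendment. The specimen review in Section 7.3 already makes all of this tissue available, and Section 3.4 already plans to measure the necrotic tumor separately from the ablated zone. The pathologist would have to record results by tumor-bed region. The observed success rate may be less favourable than on a denominator that includes normal lung. The sample size of 10 and the precision figures stay as they are.
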